12.2.1 Definitions

12.2.1.1 Evaluable for objective response: Patients who exhibit objective disease progression prior to the end of cycle 1 will be considered evaluable for response. For all other patients, only those patients who have measurable disease present at baseline, have received at least one cycle of therapy, and have had their disease re-evaluated will be considered evaluable for response.

12.2.1.2 Evaluable Non-Target Disease Response: Patients who have lesions present at baseline that are evaluable but do not meet the definitions of measurable disease, have received at least one cycle of therapy, and have had their disease re-evaluated will be considered evaluable for non-target disease. The response assessment is based on the presence, absence, or unequivocal progression of the lesions.

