1.2 Secondary Aim

- 1.2.1 To preliminarily define the antitumor activity of ABI-009 in combination with temozolomide and irinotecan within the confines of a Phase 1 study.

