2.4.1 Prior Experience in Children

There have been no pediatric studies of ABI-009.

2.5 **Overview of Proposed Pediatric Study**

We propose to conduct a Phase 1 study of ABI-009 in children with relapsed/refractory solid tumors using the rolling 6 design. Cycle 1 will aim to establish tolerability and safety and to

obtain pharmacokinetics of ABI-009 as a single agent dosed on days 1 and 8 of a 21-day cycle. Additionally, Cycle 2+ will aim to determine the MTD and/or RP2D of ABI-009 in combination with temozolomide and irinotecan. The ABI-009 starting dose will be 35 mg/m² as a single agent during Cycle 1, while Cycle 2+ dosing and scheduling in combination with irinotecan (90 mg/m²) and temozolomide (125 mg/m²) will mimic the Phase 1 pediatric trial ADVL0918.²³

2.6 Rationale for Amendment #4 (Addition of Dose Level -2 and modification of the definition of hematological DLT)

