4.0 PATIENT ELIGIBILITY

All clinical and laboratory studies to determine eligibility must be performed within 7 days prior to enrollment unless otherwise indicated. Laboratory values used to assess eligibility must be no older than seven (7) days at the start of therapy. Laboratory tests need **not** be repeated if therapy starts **within** seven (7) days of obtaining labs to assess eligibility. If a post-enrollment lab value is outside the limits of eligibility, or laboratory values are older than 7 days, then the following laboratory evaluations must be re-checked within 48 hours prior to initiating therapy: CBC with differential, bilirubin, ALT (SGPT) and serum creatinine. If the recheck is outside the limits of eligibility, the patient may not receive protocol therapy and will be considered off protocol therapy. Imaging studies must be obtained within 14 days prior to start of protocol therapy (repeat the tumor imaging if necessary).

Clarification in timing when counting days: As an example, please note that if the patient's last day of prior therapy is September 1st, and the protocol requires waiting at least 7 days for that type of prior therapy, then that patient cannot be enrolled until September 8th.

Important note: The eligibility criteria listed below are interpreted literally and cannot be waived (per COG policy posted 5/11/01). All clinical and laboratory data required for determining eligibility of a patient enrolled on this trial must be available in the patient's medical or research record which will serve as the source document for verification at the time of audit.

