- ¹² Patients experiencing progressive disease (defined in Section 12.6.4) in Cycle 1 can continue to Cycle 2 as long as 1) they have not experienced a DLT in Cycle 1, 2) they have not met any off study criteria listed in section 10.2, and 3) they meet all guidelines established in section 5.2. Patients must have at least stable disease to continue to Cycles 3 and later.

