12.7 Best Response

12.7.1 Evaluation of Best Overall Response

The best overall response is the best response recorded from the start of the treatment until disease progression/recurrence (taking as reference for progressive disease the smallest measurements recorded since the treatment started). The patient's best response assignment will depend on the achievement of both measurement and confirmation criteria.

Table 1. Sequences of overall response assessments with corresponding best response.

1 st Assessment	2 nd Assessment	Best Response
Progression		Progressive disease
Stable, PR, CR	Progression	Progressive disease
Stable	Stable	Stable
Stable	PR, CR	Stable
Stable	Not done	Not RECIST classifiable
PR	PR	PR
PR	CR	PR
PR, CR	Not done	Not RECIST classifiable
CR	CR	CR

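### The response-evaluable rule for the combination's antitumor activity admits patients who received only single-agent ABI-009 in Cycle 1, and classes Cycle 1 progressors as progressive disease whatever happens on the combination

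*Combined protocol and SAP*

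**What the plan says.** Section 1.2.1 states the secondary aim: "To preliminarily define the antitumor activity of ABI-009 in combination with temozolomide and irinotecan within the confines of a Phase 1 study". Section 2.5 gives Cycle 1 a different purpose, to establish tolerability and "obtain pharmacokinetics of ABI-009 as a single agent dosed on days 1 and 8 of a 21-day cycle"; then "Cycle 2+ will aim to determine the MTD and/or RP2D of ABI-009 in combination with temozolomide and irinotecan". Section 5.1 agrees: temozolomide and irinotecan are first given in Cycle 2.

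Section 12.2.1.1 gives two routes to being response-evaluable. The first is early progression: "Patients who exhibit objective disease progression prior to the end of cycle 1 will be considered evaluable for response". The second covers all other patients with measurable disease at baseline who "have received at least one cycle of therapy, and have had their disease re-evaluated will be considered evaluable for response". Section 12.2.1.2 uses the same one-cycle condition for non-target disease.

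On timing, Section 4.0 says "Imaging studies must be obtained within 14 days prior to start of protocol therapy", and the Section 8.1 table schedules disease evaluation at the end of Cycle 1 and again at the end of Cycle 2. Response is measured against the pre-treatment reference for RECIST (12.2.2.4, 12.2.4.1), MIBG (12.4.3) and CNS disease (12.6.4). Section 12.7.1 sets the window: "The best overall response is the best response recorded from the start of the treatment until disease progression/recurrence". Footnote 12 of Section 8.1 adds: "Patients experiencing progressive disease (defined in Section 12.6.4) in Cycle 1 can continue to Cycle 2 as long as" three conditions are met. Section 11.5 says only that response is reported descriptively.

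**The concern.** The aim names a three-drug regimen, but the rule for who counts, and the window for best response, both start with one drug. No section defines a set of patients treated with the combination. Two things follow.

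First, patients who left during or after Cycle 1 without temozolomide or irinotecan can appear in the response summary for the combination. Second, a patient who grew on ABI-009 alone and then received the combination cannot be recorded as responding to it.

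What is at stake is interpretation. The summary would describe ABI-009 alone followed by the combination. A reader may well set it beside the figures in Section 2.1.4: 8 responses in 50 patients (16%) on irinotecan and temozolomide, and 6 in 71 (8.5%) with temsirolimus added.

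**Working it through.** The documents state no response rate, target rate or response sample size, so there is no figure to reproduce. The check compares the rules and then illustrates their effect. All tumor sizes and responder counts below are assumptions.

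**1. Can a patient be evaluable with no combination dose?**
- Early-progression route: progression must come before the end of Cycle 1, so the qualifying event always precedes the combination.
- One-cycle route: Cycle 1 plus the scheduled end-of-Cycle-1 evaluation is enough.

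The answer is yes by either route.

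**2. What happens to a Cycle 1 progressor who continues?**
In the 12.7.1 table, progression at the first assessment gives a best response of progressive disease, whatever follows. Take RECIST sums of 100 mm (pre-study), 122 mm (end of Cycle 1) and 80 mm (on the combination):
- Cycle 1 change: 122/100 − 1 = +22%, and +22 mm, so PD under 12.2.4.1 (at least 20% and 5 mm).
- Change from pre-study: 80/100 − 1 = −20.0%.
- Change on the combination: 80/122 − 1 = −34.4%.
- Best response: PD.

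The CNS criteria in 12.6.4 use products of diameters with other thresholds, but the first row of the 12.7.1 table acts in the same way.

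**3. Can Cycle 1 shrinkage enter a combination response?**
Yes, in part. With sums of 100, 85 and 69 mm, the change from pre-study is 69/100 − 1 = −31.0% (PR size), while the change on the combination is 69/85 − 1 = −18.8%. The opposite also occurs: sums of 100, 115 and 78 mm give −22.0% from pre-study and 78/115 − 1 = −32.2% on the combination.

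**4. Is an end-of-Cycle-1 SD, PR or CR credited by itself?**
No. In the 12.7.1 table, any of these followed by no second assessment is not classifiable, and followed by progression is PD. On the Section 8.1 schedule the second assessment is at the end of Cycle 2, after the combination has started.

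**5. Denominator.**
Let N be the patients summarized, k those with Cycle 1 only, and R the responders, all assumed to be among the combination-treated. The rates are R/N and R/(N − k). N is set to the additional enrollment in Section 11.1.1: 18 projected, 26 maximum. R = 2.

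| N | k | R/N | R/(N − k) |
|---|---|---|---|
| 18 | 2 | 11.1% | 2/16 = 12.5% |
| 18 | 5 | 11.1% | 2/13 = 15.4% |
| 18 | 10 | 11.1% | 2/8 = 25.0% |
| 26 | 5 | 7.7% | 2/21 = 9.5% |
| 26 | 8 | 7.7% | 2/18 = 11.1% |
| 26 | 14 | 7.7% | 2/12 = 16.7% |

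The largest k for each N applies 7/13 = 54%, the share called inevaluable at Dose Level -1 in Section 2.6. The documents do not say why those patients were inevaluable or whether they reached Cycle 2, so this is only an assumed outer bound.

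**The case against.** The strongest reply has four parts.

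- **The aim is modest.** It is preliminary, confined to a Phase 1 study and reported descriptively. No pooled percentage is specified. This stands, and it limits the point to interpretation.
- **The numbers are imprecise anyway.** Exact 95% intervals are 1.4% to 34.7% for 2/18 and 1.9% to 45.4% for 2/13. This also stands. The case rests on which regimen the summary describes; it does not claim a detectable difference in rate.
- **Counting early progressors is conservative.** Restricting to combination-treated patients removes early failures and, for a fixed number of responders, can only raise the rate. Entry to Cycle 2 after progression is also selective: it requires no Cycle 1 DLT and meeting Section 5.2. This stands, and is why the all-treated summary should stay.
- **A pre-treatment baseline is the plan's consistent reference.** Re-basing after growth makes a 30% fall easier to reach. This stands too; the baseline should not be replaced.

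A reader might go further and infer that any stability or shrinkage seen at the end of Cycle 1 is credited to the combination. The documents do not support that: without a second assessment such a result is not classifiable under 12.7.1. What remains is that Cycle 1 shrinkage can contribute to a response later confirmed on the combination.

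**Conclusion.** The mismatch between aim 1.2.1 and Section 12.2.1.1 is real. As written, patients with no combination dose enter the response summary, and a Cycle 1 progressor who continues is PD regardless of the outcome on the combination. The size cannot be taken from the documents. Under the assumed counts above, 11.1% becomes 12.5% to 25.0% with N = 18, and 7.7% becomes 9.5% to 16.7% with N = 26. It is zero if every patient receives the combination.

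It would be wrong to conclude that the trial's dose finding is affected. The analysis is descriptive, and no power, sample size or dose decision depends on it. It would also be wrong to call the pre-study baseline an error.

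How many patients the second consequence touches depends on text that conflicts. Section 5.2 requires at least stable disease only from Cycle 3, and footnote 12 lets Cycle 1 progressors continue but defines progression by Section 12.6.4, which covers CNS tumors only. The schema text and Section 10.1(a) list progression as a reason to stop, with no such exception. These passages must be reconciled.

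**What to change.** 1. Keep the all-treated response summary with the pre-study baseline.
2. In 12.2.1.1 and 11.5, add a set for aim 1.2.1: patients who received at least one dose of the Cycle 2 combination and were then re-evaluated, or who progressed or died after that dose (counted as non-responders). Align 12.2.1.2.
3. List patients with Cycle 1 only separately, as single-agent outcomes.
4. Flag Cycle 1 progressors who went on to the combination.
5. Optionally show change from the end-of-Cycle-1 scan as a supplementary description, with a printed caution that re-basing after growth makes a 30% fall easier to reach.
6. Reconcile Section 5.2, footnote 12 of Section 8.1 (with its reference to 12.6.4), the schema text and Section 10.1(a).

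The cost is wording and some added table rows or columns. No new scans are needed, because the end-of-Cycle-1 evaluation is already scheduled. The downsides to state in the report are a smaller denominator and a combination-treated set that leaves out early failures and so can raise the apparent rate; for that reason the two summaries should be shown together.

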Amylase, Lipase	X	Prior to Cycle 2	X
Pregnancy Test ²	X		
Tumor Disease Evaluation	X	End of Cycles 1 ¹² & 2	Every other cycle x 2 then q 3 cycles ⁵
Bone Marrow Evaluation ⁷	X		
Medication Diary ⁶		Cycle 2	X
Oxygen Saturation	X	Weekly	X ⁸
Tumor Tissue Studies ⁹	X		

[^] Studies may be obtained within 72 hours prior to the start of the subsequent cycle.

¹ See [Section 8.3](#) for timing of PK studies.

² Women of childbearing potential require a negative pregnancy test prior to starting treatment; sexually active patients must use an acceptable method of birth control. Abstinence is an acceptable method of birth control.

³ If patients have Grade 4 neutropenia then CBCs should be checked at least every 2-3 days until recovery to Grade 3 or until meeting the criteria for dose limiting toxicity.

⁴ If patients develop Grade 4 neutropenia or Grade 4 thrombocytopenia then CBCs should be checked every 3 to 4 days until recovery to Grade 3

⁵ Tumor Disease Evaluation should be obtained on the next consecutive cycle after initial documentation of either a PR or CR. Subsequent scans may restart 2 cycles after the confirmatory scan. Please note that for solid tumor patients, if the institutional investigator determines that the

- patient has progressed based on clinical or laboratory evidence, he/she may opt not to confirm this finding radiographically.
- ⁶ Medication diary (see [Appendix IX](#)) should be reviewed after completion of each treatment cycle and uploaded into RAVE.
- ⁷ As appropriate for disease, to confirm bone marrow involvement at enrollment, or as clinically indicated.
- ⁸ Required prior to each cycle; weekly for subsequent cycles only if clinically indicated.
- ⁹ See [Section 8.4](#) and [Appendix XII](#) for details of Tumor Tissue studies.
- ¹⁰ If Grade 3 or 4 hypercholesterolemia or Grade 3 or 4 hypertriglyceridemia is detected when routine (non-fasting) laboratory studies are performed, the tests should be repeated within 3 days in the fasting state to permit accurate grading.
- ¹¹ If the initial blood glucose is a random sample that is outside of the normal limits, then follow-up fasting blood glucose can be obtained and must be within the upper normal limits for age. If blood glucose is $\geq 250 - 500$ mg/dL or $> 13.9 - 27.8$ mmol/L when routine (non-fasting) laboratory studies are performed, the test should be repeated within 3 days in the fasting state to permit accurate grading.

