10.0 CRITERIA FOR REMOVAL FROM PROTOCOL THERAPY AND OFF STUDY CRITERIA

10.1 Criteria for Removal from Protocol Therapy

- a) Clinical (including physical examination or serum tumor markers) or radiographic evidence of progressive disease (See [Section 12.0](#)).

- b) Adverse Events requiring removal from protocol therapy (See [Section 6.0](#)).
- c) Refusal of protocol therapy by patient/parent/guardian
- d) Non-compliance that in the opinion of the investigator does not allow for ongoing participation.
- e) Completion of 35 cycles of therapy.
- f) Physician determines it is not in the patient's best interest.
- g) Repeated eligibility laboratory studies (CBC with differential, bilirubin, ALT (SGPT) or serum creatinine) are outside the parameters required for eligibility prior to the start of ABI-009 (See [Section 8.1](#)).
- h) Study is terminated by Sponsor.
- i) Pregnancy

Patients who are removed from protocol therapy during cycle 1 should continue to have the required observations in [Section 8.1](#) until the originally planned end of the cycle or until all adverse events have resolved per [Section 13.4.4](#), whichever happens LATER. The only exception is with documentation of the patient's withdrawal of consent. Patients who are removed from protocol therapy in subsequent cycles should have the necessary observations to ensure adequate clinical care.

Patients who are off protocol therapy are to be followed until they meet the criteria for Off Study (see below). Ongoing adverse events, or adverse events that emerge after the patient is removed from protocol therapy, but within 30 days of the last dose of investigational agent, must be followed and reported via RAVE and CTEP-AERS (if applicable). Follow-up data will be required unless consent is withdrawn.

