12.2.5 Overall Response Assessment

Table 1: For Patients with Measurable Disease (i.e., Target Disease)

Target Lesions	Non-Target Lesions	New Lesions	Overall Response	Best Overall Response when Confirmation is Required*
CR	CR	No	CR	≥ 28 days Confirmation
CR	Non-CR/Non-PD	No	PR	≥ 28 days Confirmation
CR	Not evaluated	No	PR	
PR	Non-CR/Non-PD/not evaluated	No	PR	
SD	Non-CR/Non-	No	SD	documented at least once ≥ 28 days from baseline

	PD/not evaluated			
PD	Any	Yes or No	PD	no prior SD, PR or CR
Any	PD**	Yes or No	PD	
Any	Any	Yes	PD	

* See RECIST 1.1 manuscript for further details on what is evidence of a new lesion.
 
** In exceptional circumstances, unequivocal progression in non-target lesions may be accepted as disease progression.
 
Note: Patients with a global deterioration of health status requiring discontinuation of treatment without objective evidence of disease progression at that time should be reported as “symptomatic deterioration.” Every effort should be made to document the objective progression even after discontinuation of treatment.
				

Table 2: For Patients with Non-Measurable Disease (i.e., Non-Target Disease)

Non-Target Lesions	New Lesions	Overall Response
CR	No	CR
Non-CR/non-PD	No	Non-CR/non-PD*
Not all evaluated	No	not evaluated
Unequivocal PD	Yes or No	PD
Any	Yes	PD

* ‘Non-CR/non-PD’ is preferred over ‘stable disease’ for non-target disease since SD is increasingly used as an endpoint for assessment of efficacy in some trials so to assign this category when no lesions can be measured is not advised
		

Table 3: Overall Response for Patients with Neuroblastoma and Measurable Disease

CT/MRI	MIBG	Bone Scan	Bone Marrow	Catechol	Overall
PD	Any	Any	Any	Any	PD
Any	PD	Any	Any	Any	PD
Any	Any	PD	Any	Any	PD
Any	Any	Any	PD	Any	PD
SD	CR/PR/SD	Non-PD	Non-PD	Any	SD
PR	CR/PR	Non-PD	Non-PD	Any	PR
CR/PR	PR	Non-PD	Non-PD	Any	PR
CR	CR	Non-PD	Non-PD	Elevated	PR
CR	CR	CR	CR	Normal	CR

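### Section 12.2.1.1 can drop treatment failures from the response denominator, mainly children who leave during Cycle 1 before any disease re-evaluation

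*Combined protocol and SAP*

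**What the plan says.** **Who is evaluable (Section 12.2.1.1).** Route 1: "Patients who exhibit objective disease progression prior to the end of cycle 1 will be considered evaluable for response". Route 2, for everyone else, is limited to children with measurable disease at baseline who "have received at least one cycle of therapy, and have had their disease re-evaluated will be considered evaluable for response". Neither the word objective nor the method of re-evaluation is defined there.

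**How a child can leave.** Section 10.1(a) ends protocol therapy on "Clinical (including physical examination or serum tumor markers) or radiographic evidence of progressive disease". Footnote 5 to the Section 8.1 table says, for solid tumor patients, that if the investigator judges that the "patient has progressed based on clinical or laboratory evidence, he/she may opt not to confirm this finding radiographically". Section 10.1 also lists adverse events and refusal among the reasons for removal.

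**When disease is assessed.** The Section 8.1 table schedules a tumor evaluation at the "End of Cycles 1" and 2. The later-cycle cell reads "Every other cycle x 2 then q 3 cycles", and this is the cell that carries footnote 5.

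**What is asked after removal.** Section 10.1: "Patients who are removed from protocol therapy during cycle 1 should continue to have the required observations in" Section 8.1, at least to the planned end of that cycle unless consent is withdrawn. After removal in later cycles, only the observations needed for adequate clinical care are asked for. The note in Section 12.2.5, on children who deteriorate without objective progression, adds: "Every effort should be made to document the objective progression even after discontinuation of treatment".

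**How response is classified and reported.** Section 12.2.6 assigns a best response to each patient and refers to Section 12.8, but Section 12 ends at 12.7. In the Section 12.7.1 table, a first assessment of stable followed by no second assessment is not classifiable under RECIST. Section 11.5 promises a descriptive report and names no denominator.

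**The concern.** A child who was never re-evaluated cannot be a documented responder. Leaving such children out therefore shrinks the denominator and never the numerator. When the reason for leaving is clinical decline, toxicity or death, the exclusion depends on outcome.

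What is at stake is the trial's only secondary aim, a preliminary view of the antitumor activity of ABI-009 with temozolomide and irinotecan (Section 1.2.1). Because Section 11.5 gives no denominator, Section 12.2.1.1 is the only working definition a report could use. Numbers at any one dose level will be small, so one or two omitted failures visibly move the percentage.

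**Working it through.** **Step 1. Is there a figure to reproduce?** No. The documents give no response rate, response denominator or interval. The planned numbers in Section 11.1.1 serve only to scale an illustration: 6 + 6 = 12 evaluable children at Dose Level -2, and 18 already enrolled + 18 more = 36 as the expected maximum. Those counts allow for inevaluability for toxicity, not for response.

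**Step 2. Run the typical exits through the rules.**

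| Child with measurable disease | Section 12.2.1.1 | Section 12.7.1 table |
|---|---|---|
| Declines clinically in Cycle 1, never re-evaluated | Not route 1 (nothing objective documented), not route 2 | No row |
| Toxicity exit or death in Cycle 1 before re-evaluation | Neither route | No row |
| Stable at end of Cycle 1, then declines clinically, no second assessment | Evaluable by route 2 | Not classifiable, rather than a failure |
| Objective progression before the end of Cycle 1 | Evaluable by route 1 | Progressive disease |
| Withdraws consent before re-evaluation | Neither route | No row; outcome unknown |

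The first two rows are failures with no place in the denominator. The third is admitted by one section and left without a category by another, and the plan does not say whether such children stay in the denominator. Route 1 also carries no measurable-disease condition, so an early progressor without measurable disease is counted although a comparable child on route 2 would not be.

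**Step 3. Size.** With r responders among N children and k non-responders dropped, the rate goes from r/N to r/(N-k), a factor of N/(N-k). Neither k nor r is in the documents. I assume that 10% to 40% are lost and, for simplicity, that all N have measurable disease.

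- As proportions: 1/(1-0.10) = 1.11 and 1/(1-0.40) = 1.67.
- N = 12, r = 1: 1/12 = 8.3% becomes 1/11 = 9.1% (k = 1), 1/10 = 10.0% (k = 2), 1/8 = 12.5% (k = 4) or 1/7 = 14.3% (k = 5). The factor runs from 12/11 = 1.09 to 12/7 = 1.71.
- N = 36, r = 3: 3/36 = 8.3% becomes 3/32 = 9.4% (k = 4), 3/29 = 10.3% (k = 7), 3/25 = 12.0% (k = 11) or 3/22 = 13.6% (k = 14). The factor runs from 36/32 = 1.12 to 36/22 = 1.64.
- With r = 0 the point estimate stays at zero; with k = 0 nothing changes.

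**Step 4. Against sampling error.** The exact 95% interval for 1/12 is 0.2% to 38.5%, and for 1/7 it is 0.4% to 57.9%. The shift is small beside either interval.

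**The case against.** The strongest reply is that the schedule closes most of the gap for the stated aim. The aim concerns the combination, which starts only in Cycle 2, and an evaluation is due at the end of Cycle 1. A child with measurable disease who starts the combination has normally had one cycle and one re-evaluation, and so is already evaluable. Footnote 5 sits on the later-cycle cell. Footnote 12 lets a child who progresses in Cycle 1 go on to Cycle 2 under stated conditions. Section 10.1 continues the Section 8.1 observations for children removed in Cycle 1, and re-evaluation is not restricted to imaging.

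Most of this stands, and it confines the Section 12.2.1.1 gap mainly to Cycle 1 leavers. It does not close it. Continued observation cannot help after death. A child who stops part-way through Cycle 1 and is later found stable may still fail the one-cycle condition. Seeking objective progression after stopping is best effort and says nothing on how to count a child in whom it is never documented. Section 10.1(a) allows removal for clinical progression in any cycle. Classifying each patient under Section 12.2.6 points to a section that does not exist.

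Three stronger readings are tempting and are not supported:

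- *That the response rate is inflated.* No rate or denominator is specified, and counting early progressors without measurable disease would push the other way. The net direction is not established.
- *That only failures are removed.* Children who withdraw consent have an unknown outcome.
- *That early loss is known to be common, because 7 of 13 children at Dose Level -1 were inevaluable (Section 2.6).* Under Section 11.2.1, children without a DLT must receive at least 85% of the prescribed dose in each of Cycles 1 and 2 and have the required monitoring. A child can fail that and still be evaluable for response, so the figure does not measure missing re-evaluations.

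**Conclusion.** The point holds in a limited form. As written, Section 12.2.1.1 can leave out children with measurable disease who fail before any re-evaluation, mainly in Cycle 1, and the Section 12.7.1 table leaves some later failures unclassified. Taken alone, that omission can only raise the reported rate once there is at least one response. The factor is N/(N-k), about 1.1 to 1.7 if 10% to 40% are lost. That range rests on assumed losses, not on data in the documents.

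The consequence is modest: the endpoint is secondary and descriptive, the exact intervals are far wider than the shift, and the MTD and RP2D do not depend on it. It is still worth correcting, because the omission is tied to outcome and the remedy uses data already collected.

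**What to change.** In Section 12.2.1.1:

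- Make the main response denominator all children with measurable disease who received at least one dose of protocol therapy.
- Count clinical or laboratory progression, toxicity exit or death before re-evaluation as non-response, and list the reason for each.
- Report also the rate among those who started the combination in Cycle 2, since that is the secondary aim.
- Keep the re-evaluated-only rate as a supportive line.
- List consent withdrawals separately.
- Apply the measurable-disease requirement to early progressors as well.

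Then reconcile this definition with Section 12.2.6, correct the references to Section 12.8, and state how the rows of the Section 12.7.1 table with no second assessment enter the denominator.

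The cost is a short text change. It needs no extra visits, scans or patients. The reported response rate may come out slightly lower.
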